7. TRIAL DESIGN

This is an observational multicentre cohort study which will take place in a number of hospitals in Wessex. Patients will be recruited to the trial during admission for gallstone disease and followed up for 3 years after this admission. At each follow up timepoint patients will be contacted and asked to complete a quality of life questionnaire and will also be asked whether they have had any further admissions with gallstone related disease. Follow up information may also be obtained from hospital and GP records where appropriate.

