2. LAY SUMMARY

Patient over 70 are very commonly admitted to hospital with problems caused by gallstones, such as pain, infection, jaundice and pancreatitis (inflammation of the pancreas, a digestive organ which can get blocked by gallstones). Some people have their gallbladder removed during their initial admission and others are treated first with medical therapy (such as antibiotics or an endoscopy) then brought back later to have their gallbladder removed as a planned (or "elective") operative. This usually prevents further problems caused by gallstones. A third group of patients may not be offered surgery at all, usually because they are elderly, frail or have other medical problems which make surgery more risky. Very little is known about what happens to these patients – such as whether the gallstones do cause more problems and how this affects their quality of life. This study aims to follow up patients who were admitted to hospital with gallstone disease to assess how this has affected them for up to three years after their initial diagnosis and compare those who did and those who didn't have surgery. Patients will be contacted regularly to ask whether they have any ongoing symptoms and how this affects their quality of life. This is an observational study which will not affect which treatment each patient receives - this will be decided as normal by the team treating them in hospital. A better understanding of what happens to patients after surgical and nonsurgical treatment would allow doctors to have more informed discussions with patients about the likely outcomes of each treatment and improve their ability to make a joint decision about whether surgery is the best option.

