6. OBJECTIVES AND OUTCOME MEASURES

Objectives	Outcome Measures	Timepoint(s) of evaluation of this outcome measure (if applicable)
Primary Objective To compare the rate of gallstone- related hospital re-admission between patients treated operatively and non-operatively	Number and percentage of patients readmitted to hospital with gallstone-related disease by each timepoint.	30 days, 1 year, 3 years
1. To compare morbidity in operative and non-operative groups 2. To compare mortality in operative and non-operative groups 3. To compare quality of life in operative and non-operative groups	Number and percentage of patients with complications in each group Number and percentage of patients who have died in each group Gastrointestinal Quality of Life Index (GIQLI) in each group	30 days, 1 year, 3 years
Exploratory Objectives To assess the result of frailty on		

IRAS ID: 301556

morbidity, mortality and quality of	Morbidity, mortality and quality of life	30 days, 1 year, 3	l
life (as defined above)	according to Rockwood frailty score	years	l
To assess whether frailty affects	Comparison of Rockwood frailty score in		
whether or not surgery is carried	operative and non-operative groups both		
out	before and after surgery.		l
	- ,		

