12.2. Description of Statistical Methods

Continuous data will be summarized using descriptive statistics (mean, median, standard deviation, quartiles, minimum and maximum) and categorical data will be summarized using counts and

IRAS ID: 301556

percentages. The proportion of patients undergoing operative compared to non-operative treatment will be reported.

Primary endpoint

The primary endpoint will be reported as the percentage of patients re-admitted with gallstone related problems after operative vs non-operative management during their index admission.

Secondary endpoints

Data will be reported at 30 days, 1 year and 3 years. Patients who have had complications or have died in each group will be reported as a number and percentage. Comparison between groups will be carried out using Chi squared test. Gastrointestinal Quality of Life Index (GIQLI) in each group will be reported as a median and range. Paired T test will be used to compare groups.

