12.3. Sample Size Determination

From previous studies, we estimate an approximate readmission rate of at least 30% in patients who do not have surgery compared to 5% in those who do. We estimate that approximately 10% of patients over 70 will not have surgery therefore the enrolment ratio is likely to be 1:9. Using an alpha of 0.05 and a power of 0.9 the number of patients required would therefore be 260. We would aim to recruit a minimum of 290 patients to account for a maximum of 10% lost to follow up.

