12.4. Analysis Populations

All patients as registered. Comparisons will be made between groups who had surgery during/after their index admission and those who were treated non-operatively in assessing the primary endpoint.

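### The primary endpoint does not exclude planned readmission for cholecystectomy, which distorts the comparison in opposite directions under the protocol's two group definitions

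*Protocol*

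**What the plan says.** Section 6 defines the primary outcome as "Number and percentage of patients readmitted to hospital with gallstone-related disease by each timepoint", the timepoints being 30 days, 1 year and 3 years. Section 7 says how it is collected: at each contact patients are "asked whether they have had any further admissions with gallstone related disease", and hospital and GP records may also be used. The Synopsis and section 12.2 speak of gallstone-related problems rather than disease. None of these places mentions planned, elective, unplanned or emergency admission.

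The Lay Summary describes three pathways: surgery in the first admission, no surgery, and initial medical treatment of patients who are "then brought back later to have their gallbladder removed as a planned" operation.

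The groups are defined twice. Section 12.2 reports the primary endpoint "after operative vs non-operative management during their index admission". Section 12.4 compares "groups who had surgery during/after their index admission and those who were treated non-operatively in assessing the primary endpoint".

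Section 12.3 assumes a "readmission rate of at least 30% in patients who do not have surgery compared to 5% in those who do", and that "approximately 10% of patients over 70 will not have surgery therefore the enrolment ratio is likely to be 1:9". Section 12.1 states that no separate SAP is in use, so this text is the operative definition of the endpoint.

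**The concern.** A patient who comes back for a scheduled cholecystectomy has been admitted to hospital again because of gallstones. Asked the question in section 7, that patient could reasonably answer yes. The treatment being studied would then be scored as the outcome.

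The effect on the comparison depends on the group to which the patient belongs. Under section 12.4 the patient is in the operative group and raises its readmission rate. Under section 12.2 the patient was managed non-operatively in the index admission and raises that group's rate instead. The primary result could therefore be diluted or exaggerated by scheduling practice alone, and a reader could not tell which had happened.

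**Working it through.** **Inputs from section 12.3.** Non-operative rate 30%, operative rate 5%, ratio 1:9, alpha 0.05 (taken as two-sided), power 0.9, 260 patients before loss to follow-up. At 1:9 this is 26 non-operative and 234 operative.

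**The plan's own figure.** The pooled two-proportion formula with 30% in the small group gives 20.7, rounded up to 21, so 21 × 10 = 210 in total (250 with continuity correction). The stated 260 appears when 5% is attached to the small group: 25.5, rounded up to 26, × 10 = 260. This discrepancy is conservative and is not the point here. With the rates as stated, 26 vs 234 gives exact chi-squared power of 0.955 (0.94 by normal approximation), so the design meets its target if planned returns are not counted. The loss step reproduces: 260/0.9 = 289, about 290.

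**Assumptions.**
- f, the share of operated patients who return for planned surgery, is not in the protocol and is shown over a range.
- Every planned return is coded as a readmission.
- The 5% rate of other readmissions applies equally to delayed-surgery patients.
- The test is an uncorrected chi-squared test. Section 12.2 names chi-squared under the secondary endpoints; I use it for the primary as well.

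**Section 12.4 grouping (surgery during or after the index admission).** Operative rate = 1 − 0.95(1 − f), compared with 30%; exact power at 26 vs 234.

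| f | Operative rate | Difference from 30% | Power |
|---|---|---|---|
| 0 | 5.0% | 25.0 points | 0.955 |
| 5% | 9.8% | 20.3 points | 0.78 |
| 10% | 14.5% | 15.5 points | 0.52 |
| 20% | 24.0% | 6.0 points | 0.12 |
| 26.3% | 30.0% | 0 | – |
| 50% | 52.5% | −22.5 points | reversed |

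The break-even solves 1 − 0.95(1 − f) = 0.30, so f = 0.25/0.95 = 26.3%. At f = 50% the test rejects in the opposite direction with probability 0.60.

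**Section 12.2 grouping (management in the index admission).** Delayed-surgery patients move to the non-operative group, which becomes 26 + 234f patients. If each counts as readmitted, its rate is (26 × 0.30 + 234f)/(26 + 234f).
- f = 10%: (7.8 + 23.4)/(26 + 23.4) = 31.2/49.4 = 63%
- f = 30%: (7.8 + 70.2)/(26 + 70.2) = 78.0/96.2 = 81%

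Both are set against 5% in patients operated on in the index admission.

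**Section 12.2 grouping with planned returns left out.** The non-operative rate is (7.8 + 0.05 × 234f)/(26 + 234f).
- f = 10%: 8.97/49.4 = 18.2%, power about 0.81
- f = 30%: 11.31/96.2 = 11.8%, power about 0.51

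These two powers are normal approximations at the changed group sizes. Excluding planned returns therefore does not restore the 30% vs 5% contrast under this grouping; the group definition has to be settled as well.

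**The case against.** The protocol nowhere says that a planned return counts. The Synopsis and section 12.2 refer to problems, the Background to recurrent problems, and the Lay Summary asks whether gallstones go on to cause trouble. Read together, these suggest recurrence of disease rather than attendance for definitive treatment. The 5% operative rate points the same way. Section 7 also allows hospital and GP records, from which planned and emergency admissions might be told apart, and the CRF is not shown. Finally, f is undocumented and would differ between 30 days, 1 year and 3 years.

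Much of this stands. A reader might infer that the protocol scores elective surgery as a failure, or that the study will lose or reverse its contrast. The text supports neither. The first is an omission, not a stated rule. The second needs the section 12.4 grouping and f of about 26% or more; under section 12.2 the contrast grows.

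What does not stand is that the narrower reading makes the omission harmless. The outcome measure in section 6 and the question in section 7 carry no such limit. Section 13.2 gives CRF completion to a registrar at each site, and no rule tells them which reading to apply. Records can classify an admission only once the protocol says which class counts.

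**Conclusion.** The point holds as a defect of definition. The primary endpoint does not exclude planned admissions, while the protocol itself describes a pathway that produces them and a sample size assumption that leaves almost no room for them.

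The size depends on f and on the grouping. If planned returns are counted under section 12.4, power is already below the planned 0.9 at f = 5%, so the concern does not need a large f. Under section 12.2 the distortion runs the other way and is large even at f = 10%. The figures are illustrations over an assumed range, with every planned return coded as a readmission; they are not forecasts. If sites apply the narrow reading consistently and patients are grouped as in section 12.4, the design contrast is unaffected. The protocol secures neither condition.

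**What to change.** 1. In the Synopsis, section 6 and section 12.2, define the primary endpoint as unplanned (emergency) gallstone-related readmission after discharge from the index admission.
2. Record planned admissions for cholecystectomy separately, with dates, and do not count them.
3. Align the telephone question in section 7 and the CRF with this definition, and use the hospital and GP records already allowed there to classify reported admissions.
4. Reconcile sections 12.2 and 12.4 so that one group definition applies. Otherwise an emergency readmission in a patient awaiting delayed surgery still falls in different groups under the two sections. Check the section 12.3 rates and ratio against the definition chosen.
5. State how planned endoscopy is handled. That is a separate choice and this point does not settle it.

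The cost is endpoint wording, through a protocol amendment, and one CRF field. No extra visits are needed.

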8. PARTICIPANT IDENTIFICATION

8.1. Trial Participants

Participants aged 70 or over who are admitted acutely to hospital with gallstone disease (including biliary colic, cholecystitis, gallstone pancreatitis, choledocholithiasis and cholangitis)

8.2. Inclusion Criteria

- Male or Female, aged 70 years or above.
- Diagnosed with biliary colic, cholecystitis, gallstone pancreatitis, choledocholithiasis or cholangitis.
- In the Investigator's opinion, is able and willing to comply with all trial requirements.
- Willing to allow his or her General Practitioner and consultant, if appropriate, to be notified of participation in the trial.

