5. BACKGROUND AND RATIONALE

Gallstone disease is the most common surgical cause of hospital admission in developed countries¹ and the most common indication for abdominal surgery²³. The prevalence increases progressively with age ^{1,2,4}. The incidence of gallstones in those aged 80 or over is as high as 38-53%^{5,6}, and has been reported to be as high as 80% for patients over 90 years of age⁷. Older patients are known to be at greater risk of complications of gallstones than younger patients, and are more likely to present with cholecystitis, choledocholithiasis and pancreatitis⁸, as opposed to uncomplicated biliary colic. While modern guidelines^{9,10} advise surgical management of gallstone disease in the typical patient, it is unclear whether these should also apply to the elderly, who often have pre-existing conditions and diminished physiological reserve which may affect their suitability for surgery.

Currently, published reports suggest that older patients are less likely to be managed surgically, with up to 30% of older patients managed non-operatively^{11–13}. In cases where intervention is required, ERCP for ductal stones or cholecystostomy are considered. However, up to a third of patients may have recurrent problems when managed non-operatively¹⁴. Long term follow-up in these patients is lacking and there is

IRAS ID: 301556

no real data comparing mid- to long-term outcomes, readmission rates or quality of life in patients undergoing these procedures compared with the definitive management of cholecystectomy.

This study aims to investigate the differences in outcomes, readmission rates and quality of life when comparing older patients (defined as at least 70 years of age) who are admitted with acute biliary disease (including biliary colic, cholecystitis, choledocholithiasis and pancreatitis) and are treated operatively compared with those who are managed with medical treatment only.

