8.3. Exclusion Criteria

The participant may not enter the trial if ANY of the following apply:

• Participant is unwilling or unable to give informed consent for participation in the trial.

IRAS ID: 301556

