9.2. Screening and Eligibility Assessment

There is no specific time limit between screening and registration but the patient must be recruited and registered during their index hospital admission.

Screening will involve reviewing the patient's medical notes and imaging results to ensure that there is a clear diagnosis of gallstone-related disease. If the diagnosis is unclear (e.g. pancreatitis without confirmation of gallstones) the patient should either be excluded or rescreened once further investigations have been carried out. A screening log will be maintained at each site, documenting eligibility and if eligible, the reasons for patients not recruited (e.g. not approached, declined).

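### Eligibility does not require a gallbladder in situ, so patients with an earlier cholecystectomy could be registered and would usually be counted in the small non-operative group

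*Protocol*

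**What the plan says.** **Who may enter.** Section 8.2 of the protocol requires age 70 or above, ability to comply, agreement to notify the GP and consultant, and being "Diagnosed with biliary colic, cholecystitis, gallstone pancreatitis, choledocholithiasis or cholangitis". Section 8.3 has one exclusion: "Participant is unwilling or unable to give informed consent for participation in the trial". Screening under 9.2 reviews notes and imaging to "ensure that there is a clear diagnosis of gallstone-related disease". No section mentions previous cholecystectomy or asks for a gallbladder in situ. Section 9.6 names only demographic data and frailty as baseline information.

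**What is compared.** Section 5 sets ERCP and cholecystostomy against cholecystectomy, and says that data are lacking on "quality of life in patients undergoing these procedures compared with the definitive management of cholecystectomy". The lay summary describes three routes: gallbladder removed at the first admission, removed later as a planned operation, or surgery not offered. It says that the results should help doctors and patients decide jointly about surgery.

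**How patients are grouped.** Section 12.4 analyses "All patients as registered" and adds: "Comparisons will be made between groups who had surgery during/after their index admission and those who were treated non-operatively". Section 12.2 reports the primary endpoint as a percentage in each group, with no restriction or stratification. On group sizes, 12.3 says: "We estimate that approximately 10% of patients over 70 will not have surgery therefore the enrolment ratio is likely to be 1:9".

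**The concern.** Choledocholithiasis, cholangitis and gallstone pancreatitis can all occur after the gallbladder has been removed. A patient in that position meets 8.2, is not caught by 8.3 and passes 9.2. If treated by ERCP or medically, the patient is classed as non-operative, but not because surgery was weighed and declined. The operation under study had already been done.

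The non-operative readmission rate would then mix two kinds of patient: those who could have had a cholecystectomy and did not, and those for whom the choice no longer exists. Only the first kind bears on the decision described in the lay summary. The same mixture would enter the comparisons of morbidity, mortality and GIQLI. It would also enter the exploratory question in section 6 of whether frailty affects the use of surgery, which has no clear meaning for a patient without a gallbladder.

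The group that takes in these patients is expected to be small, so a few of them could be a material share of it. Because 9.6 does not name prior cholecystectomy as a baseline item, the analysis data set may not allow them to be separated later.

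**Working it through.** **Inputs from the protocol**
- Readmission 30% without surgery and 5% with it; 10% non-operative (ratio 1:9); 260 evaluable, 290 registered; alpha 0.05, taken as two-sided because 12.3 does not say (12.3).
- Up to 30% of older patients managed non-operatively in published reports (section 5).

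**Inputs assumed, because the documents give none**
- Share f of registered patients with an earlier cholecystectomy: 3%, 5% or 10%.
- Their readmission rate r: 10% to 50% in steps 2 and 3, and 5% to 40% in step 4.
- All of them are counted as non-operative.

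**1. The plan's own group size.** 260/(1 − 0.10) = 289, so 290 follows from 260. Ten per cent non-operative is 26 of 260, or 29 of 290. The 260 itself does not come out of the pooled two-sided formula in the stated direction, which gives 210, or 250 with continuity correction. That is a separate matter, and nothing below depends on it.

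**2. Share of the non-operative group.** With q the non-operative fraction among the remaining patients,

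w = 290f / [290f + q × 290(1 − f)]

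| f | Prior cholecystectomy | Other non-operative, q = 10% | w | Other non-operative, q = 30% | w |
|---|---|---|---|---|---|
| 3% | 8.7 | 28.1 | 8.7/36.8 = 24% | 84.4 | 8.7/93.1 = 9% |
| 5% | 14.5 | 27.55 | 14.5/42.05 = 34% | 82.65 | 14.5/97.15 = 15% |
| 10% | 29.0 | 26.1 | 29.0/55.1 = 53% | 78.3 | 29.0/107.3 = 27% |

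**3. Observed non-operative rate at f = 5%, true rate 30%.**
- q = 10%, r = 10%: (27.55 × 0.30 + 14.5 × 0.10)/42.05 = 9.715/42.05 = 23.1%
- q = 10%, r = 50%: (8.265 + 7.25)/42.05 = 36.9%
- q = 30%, r = 10%: (82.65 × 0.30 + 14.5 × 0.10)/97.15 = 26.245/97.15 = 27.0%
- q = 30%, r = 50%: (24.795 + 7.25)/97.15 = 33.0%

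The observed rate falls below 30% when r is below 30% and rises above it when r is higher. The sign of the bias therefore depends on a quantity the documents do not give.

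**4. Alternative: the planned 10% already includes these patients.** Hold the groups at 26 and 234, let m of the 26 have had an earlier cholecystectomy, and set p = [(26 − m) × 0.30 + m × r]/26. Power = Φ[(|p − 0.05| − 1.96 × SE0)/SE1], with SE0 the pooled and SE1 the unpooled standard error.

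With m = 0: SE0 = 0.0545, SE1 = 0.0910, and (0.25 − 0.1067)/0.0910 = 1.57, so power is 94.2%.

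| m of 26 | Observed rate, r = 5% to 20% | Power | Observed rate, r = 40% |
|---|---|---|---|
| 3 (12%) | 27.1% to 28.8% | 90.6% to 93.0% | 31.2% |
| 8 (31%) | 22.3% to 26.9% | 80.6% to 90.3% | 33.1% |
| 13 (50%) | 17.5% to 25.0% | 63.9% to 86.9% | 35.0% |

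**The case against.** The strongest reply is that the gap may have little effect. The population is deliberately broad, treatment is not influenced by the study, and the lay summary reads as if a cohort with gallbladders is intended. No document says how many post-cholecystectomy patients are admitted. With three such patients among 26, power stays above the planned 90%. If non-operative management is nearer the 30% in section 5, the shares are much smaller. Prior cholecystectomy is also a fixed fact in the notes, so it can be recovered without new data collection.

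Most of this stands, and it limits the size and urgency of the point. It does not close the gap. The lay summary is not an eligibility rule, and a fact in the notes helps only if someone is told to record and use it. The matter cannot be left to a later analysis document either: eligibility belongs in the protocol, and 12.1 says that no separate SAP is in use.

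A reader might infer more than the text supports:
- **That these patients fall automatically into the non-operative group.** Section 12.4 speaks of surgery without defining it, so an operative duct exploration could count as operative. That would also misplace the patient, since it is not the cholecystectomy being compared.
- **That they do enter and do distort the result in a known direction.** The text shows only that they could enter. The illustrated rates lie on both sides of 30%.
- **That they would make up about half of the non-operative group.** The 53% combines the highest assumed share with the lower of the protocol's two non-operative fractions. It also implies 55 of 290 (19%) non-operative, which no longer matches the planned 10%.

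**Conclusion.** The gap in the text is certain: sections 8.2, 8.3 and 9.2 let in patients who cannot have the operation under study, and 12.4 would usually place them in the non-operative group. Its effect is unknown in size and direction, because the documents give neither the frequency nor the readmission rate of these patients.

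On the assumed shares of 3% to 10%, they would form 24% to 53% of the non-operative group if 10% of the rest are non-operative, or 9% to 27% if 30% are. At a 5% share, a true 30% rate would be observed as 23% to 37% or as 27% to 33% respectively.

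The point should be fixed, because the correction is cheap and the result would otherwise be hard to interpret. It is not a fatal flaw. Confidence is high on the gap and low on its magnitude.

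**What to change.** Add previous cholecystectomy to the exclusions in 8.3, and check it during the notes and imaging review that 9.2 already requires.

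If the sponsor prefers to keep the broad population:
- add prior cholecystectomy (yes or no) to the baseline data in 9.6 and to the CRF;
- flag patients already registered from their existing notes;
- state in 12.4 that patients with a prior cholecystectomy are reported as a separate descriptive group, outside the operative versus non-operative comparison and outside the 1:9 planning ratio.

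The first option costs a one-line amendment and a small loss of accrual, limited to patients who cannot inform the comparison. The second costs one extra data item and a look back through notes. Neither changes any patient's treatment.
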